### Schedule of Assessments

	Screen.	Harv.	Treat.	1 st Follow-up				2 nd Follow-Up		Long-term	
Blinding	N/A	Double Blinding							Open 		Follow-up
Visit	1	2	3	4	5	6	ET	7	8	N/A	
Week / Month	W-7	W-5	0	M1	M3	M6	<M6	M9	M12 or Final FU 	M24	
Informed consent	X										
Medical and Medication History	X	X									
Demographic information	X										
Complete physical examination	X		X		X	X	X 	X	X	X	
Vital signs and weight	X	X	X	X	X	X	X	X	X	X	
Hematology, serum chemistry, and urinalysis 	X		X	X	X	X	X 	X	X		
Pregnancy test 	X					X	X 		X		
HIV test for Screening	X										
12-lead ECG	X		X			X	X 		X		
X-ray	X										
Eligibility confirmation	X	X									
Randomization		X									
Liposuction		X									
Injection of final drug product			X								
AE and concomitant medication assessment			X	X	X	X	X	X	X		
Records of Treatment and Medications										X	
MRI scan 	X					X	X 		X	X	
WOMAC			X	X	X	X	X 	X	X	X	
VAS	X		X	X	X	X	X 	X	X	X	
Lysholm			X	X	X	X	X 	X	X	X	
KOOS			X	X	X	X	X 	X	X	X	
IKDC			X	X	X	X	X 	X	X	X	
Quality of Life (RAND-36)			X		X	X	X 	X	X	X	

1. See Appendix 1 for the complete list of laboratory tests
2. Serum pregnancy test is performed for all females of childbearing potential (please refer to the relevant inclusion criteria)
3. May be performed the day of Visit 2 or after due to scheduling or re-scanning.
4. Performed only if the early termination is after V3.
5. Performed only if the early termination is after V4.
6. Performed if the follow-up is discontinued after V6.
7. Only for JointStem group.

## Glossary and Abbreviations

AdMSC	Adipose Tissue Derived Mesenchymal Stem Cell
AE	Adverse Event
ANCOVA	Analysis of Covariance
BMI	Body Mass Index
CFR	Code of Federal Regulations
eCRF	Electronic Case Report Form
ICH	International Conference of Harmonization
IKDC	International Knee Documentation Committee
IRB	Institutional Review Board
ITT	Intent-to-Treat
KOOS	Knee Injury & Osteoarthritis Outcome Score
LOCF	Last Observation Carried Forward
PP	Per Protocol
PT-INR	Prothrombin Time - International Normalized Ratio
SAE	Serious Adverse Event
VAS	Visual Analog Scale
WOMAC	Western Ontario and McMaster Universities Arthritis Index

## 1. PURPOSE OF STUDY

The purpose of this study is to evaluate the efficacy and safety of autologous adipose tissue derived mesenchymal stem cells (AdMSC) for the treatment of osteoarthritis.

## 2. BACKGROUND AND INDICATION

### 2.1 What is Osteoarthritis (Degenerative Arthritis)

Osteoarthritis is a group of mechanical abnormalities involving degradation of joints, including articular cartilage and subchondral bone. Symptoms may include joint pain, tenderness, stiffness, locking, and sometimes an effusion. When bone surfaces become less well protected by cartilage, bone may be exposed and damaged. As a result of decreased movement secondary to pain, regional muscles may atrophy, and ligaments may become more lax.Wei 2002, Conaghan 2008

Osteoarthritis is the most common form of arthritis, and the leading cause of chronic disability in the United States. It affects about 27 million people in the United States. Eighty percent of Americans develop osteoarthritis by age 65. Twenty-five percent of all patients of osteoarthritis visit to primary care physicians in the US. The total cost of osteoarthritis living with this disease is approximately \$5,700 annually per person.Maetzel 2004 Osteoarthritis costs the US economy nearly \$128 billion per year in medical care and indirect expenses, including lost wages and production. As population aging progresses and as more young people start taking up active sports, the size of the target patient group is growing.

### 2.2 Current Treatment for Osteoarthritis and Their Pitfalls

The cartilage is a unique avascular, aneural tissue that has limited capacity of self-repair once damaged. Despite ongoing research, treatments to manage the disease remain merely symptom-relieving, designed to control pain, and improve function and quality of life limiting adverse events. An effective treatment for cartilage defects is yet to be discovered.

Treatment generally involves a combination of lifestyle modification, analgesics, nonsteroidal anti-inflammatories, and joint injections with steroids or hyaluronan (lubricant). If pain becomes debilitating, joint replacement surgery may be used to improve the quality of life, e.g. partial joint resurfacing (hip and shoulder), and total joint replacement (hip and knee).Conaghan 2008 Although various treatments are currently in use, none of them is to address the root of cause—cartilage regeneration. In other words, there has been no cure for osteoarthritis till today.

As a way of regenerating the damaged or defective cartilage tissue, treatment of localized damage to articular cartilage using autologous chondrocytes is currently under review. A few studies are marketing this method of treatment named “autologous chondrocyte transplant”.Wysocka 2010, Hahn 2010 The treatment involves the extraction of healthy cartilage tissue from the patient which is then cultured and transplanted into the damaged site. However, this treatment requires the extraction of

chondrocytes directly from the patient and thus causes new damages in healthy articular cartilage. Also, “autologous chondrocyte transplant” cannot be applied to large lesions. Moreover, the effect is not satisfactory in patients over 40 years old whose cellular regeneration is slowed-down due to aging.

Thus, autologous chondrocyte transplant is rather limited in the number of cells harvested and their activation level and is therefore restricted in terms of treatment site, severity of the condition, and the size of lesion. Generally speaking, there was no therapy available till today to regenerate cartilage for adult.

### 2.3 Potential Use of Stem Cells in Treatment of Osteoarthritis

Over the last ten years, great progresses have been made worldwide in the adult stem cell field.Zuk 2010 Because of their unlimited capacity for self-renewal and ability to differentiate into multiple lineages, human stem cells are a potentially powerful and revolutionary tool for repair of cartilage defects. Among different origins of stem cells, marrow-derived stem cells have been considered as pluripotency of mesenchymal stem cells and proved being successful in many clinical trials.Jiang 2002

However, marrow-derived stem cells are limited and not quite easy to access. Recently many groundbreaking articles have been published describing new adult stem cell populations from many tissues which were not expected to find stem cells, such as skin, liver, digestive epithelium, dental pulp and hair follicles and the adipose tissue derived stem cell has become one of the most popular adult stem cell populations being used in the stem cell field.

There are many advantages in using AdMSCs than stem cells isolated from other sources. Firstly, unlike embryonic stem cells, the use of adult AdMSCs in research and therapy is not considered to be controversial as they are derived from adult tissue samples rather than destroyed human embryos. Secondly, adipose tissues represent an abundant and accessible source of adult stem cells, especially with the fact that overweight is a common condition in the United States, 68% of the American adult population is considered either overweight or obese. Even for normal body weight persons and most very lean individuals, 5-20 mL extraction of adipose tissue is not a problem at all. Compared with marrow-derived stem cells, more people accept collecting stem cells via lipoaspirate than bone marrow punctuation. Thirdly, AdMSCs are true stem cells with the capacity of differentiating into multi-lineage mesodermal cells and possible ectodermal and endodermal cells.Zuk 2010, Stream 2005

Finally, autologous cells are obtained from the same individual to whom they will be re-implanted. Since the AdMSCs come from the patient's own body, it has no incidence of graft-versus-host rejection and less possibilities of pathogen transmission due to the donor and recipient being the same individual. Moreover, treatments using stem cells do not cause damage as "autologous chondrocyte transplant" would do to healthy articular cartilage, as AdMSC treatment doesn't require the harvesting of healthy cartilage tissues from the patients.

## **2.4 Current Clinical Trials of Treating Osteoarthritis with Stem Cells**

There are no clinical trials to date that have been reported in the USA for humans using AdMSC to treat osteoarthritis. Several trials for osteoarthritis treatment using bone marrow derived stem cells or umbilical cord blood-derived mesenchymal stem cells are currently registered at the NIH clinical trials database. In South Korea, the sponsor completed Phase I and II clinical trials for osteoarthritis treatment with injection of autologous AdMSCs, which was proved as a safe and effective way and actually regenerated healthy cartilage tissue.

Since there is no therapy available today to regenerate cartilage so to effectively treat osteoarthritis, this clinical research has been planned in the USA under the strict regulations required by US FDA and IRB, in order to prove the efficacy and safety of AdMSC in the treatment of osteoarthritis joint and regeneration of cartilage.

### **3. INVESTIGATIONAL PLAN**

#### **3.1 Study Design**

This is a double-blind, randomized, controlled study to evaluate the efficacy and safety of JointStem for the treatment of osteoarthritis. Two or three investigational centers may be utilized in the United States so that a total of approximately 30 subjects will be randomized.

#### **3.2 Selection of Study Population**

The study population will be males or females, aged 22 to 60, who have radiographic evidence of grade 3 to 4 osteoarthritis based on the Kellgren and Lawrence radiographic criteria.

##### **3.2.1 Inclusion Criteria**

- 1) Subject who can give written informed consent
- 2) Male or female of any race, aged 22-60
- 3) Subject who had osteoarthritis of knee diagnosed at least six months prior to Screening
- 4) Subject who has joint pain  $\geq$  40mm on VAS (Visual Analog Scale) at Screening
- 5) Subject who has swelling, tenderness and active range of motion  $\geq$  Grade I at Screening
- 6) Subject who seeks invasive interventions of intra-articular injections
- 7) Subject who is willing to discontinue all pain medications for osteoarthritis except rescue medication (< acetaminophen 3.25 g per day) at least 72 hours prior to screening and throughout the duration of study
- 8) Subject who has radiographic evidence of grade 3 to 4 osteoarthritis based on the Kellgren and Lawrence radiographic criteria.
- 9) Female subject who meets one of the following criteria
  - a. Female subject of non-childbearing potential:
    - Post-menopausal for at least 6 months; or
    - Surgically sterile

b. Female patients of child-bearing potential:

- Neither pregnant nor lactating; and
- Abstinent or use adequate contraception (2 forms of birth control, one of which must be a barrier method)

10) Subject who is able to comply with lifestyle guidelines, scheduled visits, treatment plan, laboratory tests, and other study procedures

### **3.2.2 Exclusion Criteria**

- 1) Subject who has Body Mass Index (BMI)  $> 35 \text{ kg/m}^2$
- 2) Subject who has unstable knees
- 3) Subject who took any NSAID within two weeks from Screening
- 4) Subject who had any intra-articular injection therapy in any joint within 2 months from Screening
- 5) Subject who has any clinically significant disease, which is judged by the investigator to affect this clinical trial, including but not limited to diabetes not adequately controlled, bleeding diathesis or hematologic disease, endocrinopathies, cardiovascular disease, renal disease (severe renal impairment), autoimmune disease, inflammatory arthritides, and current infectious disease
- 6) Subject who has inflammatory arthropathy (rheumatoid, psoriatic, or avascular necrosis), and post traumatic or septic arthritis
- 7) Subject who has chondrocalcinosis, Paget's disease, Villonodular synovitis, and other non-OA joint diseases
- 8) Subject who has HIV/viral hepatitis
- 9) Subject who had knee surgery or radiation therapy in the affected joint within 6 months from Screening
- 10) Subject who had CVA attack within 6 months from Screening

- 11) Subject for whom the investigator judges the liposuction can cause any problem
- 12) Subject who has significant lab abnormalities for the following parameters (If a value is within 10% of the listed laboratory exclusion criterion value and the value is considered not to be clinically significant by the investigator, the subject can be considered for enrollment):
  - Serum ALT and AST > 2 x upper limit of normal
  - Serum creatinine out of normal range
  - PT/INR out of normal range
  - Hemoglobin < 10 g/dL for female subject and hemoglobin < 11 g/dL for male subject
  - Platelets out of normal range
- 13) Subject who has history of local anesthetic allergy
- 14) Subject who took immunosuppressants such as Cyclosporin A or azathioprine within 6 weeks from Screening
- 15) (If a subject uses aspirin or plavix) Subject for whom it is determined that it would not be safe to stop the aspirin/plavix therapy for 2 weeks prior to Visit 2
- 16) Subject who uses anticoagulants which cannot be stopped or corrected
- 17) Subject who had oral or intra-muscular corticosteroids within 30 days from Visit 2
- 18) Subject who had intra-articular corticosteroid injection in any joint within 30 days from Visit 2
- 19) Subject who had intra-articular hyaluronic acid injection within 30 days from Visit 2
- 20) Subject who has known hypersensitivity (allergy) to hyaluronan (sodium hyaluronate) preparations
- 21) Subject who has knee joint infections or skin diseases or infections in the area of the injection site
- 22) Subject who is an active drug/EtOH abuser
- 23) Subject who was enrolled in any other clinical trials within 2 months from Screening

- 24) Subject who the principal investigator considers inappropriate for the study due to any other reasons than those listed above
- 25) Subject whose MRI scan results during the screening period do not demonstrate any sign of cartilage damage.

### **3.3 Removal of Subjects from Study**

Subjects may be withdrawn from the study for the following reasons:

- At their own request or at the request of their legally acceptable representative
- If, in the investigator's opinion, continuation in the study would be detrimental to the subject's well-being
- At the specific request of the sponsor

Also, subjects must be withdrawn for the following reasons:

- A significant violation of the protocol, as determined by the sponsor or the investigator
- Highly significant abnormalities in the laboratory results (Highly significant abnormalities generally follow lab related exclusion criteria, but a PI can determine the high significance on any abnormalities for the safety of subject)
- Use of any other investigational drugs (including placebo)
- Subjects enrolled in the current trial but taking any prohibited medication/therapy stated in the inclusion/exclusion criteria that, in the investigator's opinion, will interfere with the study outcome.
- Subject enrolled in the current trial but having a baby

If a subject prematurely withdraws from the study, the subject must return to the clinical site for the early termination visit. In all cases, the reason for withdrawal must be recorded in the electronic Case Report Form (eCRF) and in the subject's medical records.

Contact will be maintained with subjects who are removed due to an adverse event (AE) until it has been resolved or stabilized, and the information will be documented in the eCRF and in the subject's medical records.

### **3.4 Premature Termination of Study / Closure of Center**

The sponsor has the right to terminate this study, and the investigator/sponsor has the right to close a clinical site, at any time, although this should occur only after consultation between involved

parties; the IRB must be informed in any case. Should the clinical site be closed prematurely, all study materials (equipment, study medication, etc.) must be returned to the sponsor.

This study will discontinue due to medical or administrative reasons such as:

- Serious adverse events probably related to study drug administration so that the use of study drug may no longer be justifiable
- 2 or more deaths are observed during any point in the trial
- 5 or more adverse drug reactions (NCI-CTCAE  $\geq$  Grade 3) on the injected joint are observed during any point in the trial
- Significant change of benefit-risk ratio for the subjects
- Sponsor discontinues the investigation of JointStem for the treatment of osteoarthritis or determines that the doses being studied are no longer justifiable

Possible reasons for closing of a clinical site include the following:

- The investigator feels that the number or severity of adverse events is excessive
- A change of technical, administrative, or personal circumstances occurs and the conduct of the study no longer meets ICH-GCP guidelines
- In case of evident, significant non-compliance to protocol or poor data quality

### **3.5 Treatment**

#### **3.5.1 Treatment to be Administered**

At Visit 2 (Week -5), a subject, who is qualified for this study, will be randomized to one of two study groups and the adipose tissue will be harvested via liposuction. At Visit 3 (Week 0, baseline), the randomized subject will receive a single intra-articular injection.

#### **3.5.2 Identity of Investigational Product**

JointStem is a 5 ml syringe including AdMSCs as  $1 \times 10^8$  cells/3mL and is stable at refrigerated condition up to 1 week. A positive control syringe including hyaluronic acid will be purchased and packed by the aluminum foil pack to be matched with JointStem syringe in appearance to be indistinguishable.

#### **3.5.3 End of Study**

The efficacy results will be analyzed when the last subject completes Visit 6 (6-month follow-up) and this study is finished when the last subject completes Visit 8 (12-month follow-up).

Long-term follow-up visit will be conducted to collect long-term feedbacks (records of medications and treatments) following 2 years after injection for all subjects who complete 6-month visit and accept the long-term follow-up visit.

#### **3.5.4 Selection of Dose in Study**

The dosage of JointStem was chosen through a phase 1 and 2 study conducted in South Korea.

#### **3.5.5 Choice of Control/Comparator**

This study uses hyaluronic acid as a positive control (Synvisc-One®). The purpose of using this control is to compare the efficacy of JointStem with current treatment option based on various endpoints.

#### **3.5.6 Blinding**

As this is a double-blinded study, blinding of the drug contents from the subjects, investigators, and other study personnel at each clinical site is necessary. Because two syringes of JointStem and positive control are different, one physician must be only assigned to the role of syringe injection in order to maintain the double-blinding against other site physicians and staffs.

A subject will be assigned with one randomization code on Visit 2 (Week -5). After each subject completes Visit 6 (Month 6) and the data management team confirms all individual data have no issue, the randomization code will be open for the statistical analysis.

A code-break envelope for each subject including the randomization code information will be retained by each site and can be opened, revealing the randomization information, for emergency purposes only. Investigator should note that the occurrence of a SAE should not routinely precipitate immediate unblinding. An attempt to contact the sponsor must be made prior to unblinding. If unblinding occurs, the subject must be early terminated; a written explanation must be prepared immediately.

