## Protocol Synopsis

**Title:** A Phase 2, Double-Blind, Randomized, Controlled Study to Evaluate the Efficacy and Safety of JointStem, Autologous Adipose Tissue Derived Mesenchymal Stem Cells, in Treatment of Osteoarthritis

**Phase:** Phase 2

**Indication:** Osteoarthritis (Degenerative Arthritis)

**Study Objective:** To evaluate the efficacy and safety of autologous adipose tissue derived mesenchymal stem cells (AdMSC) for the treatment of osteoarthritis

**Study Design:** This study is a double-blind, randomized, controlled study with two arms to evaluate JointStem as a treatment for subjects with osteoarthritis. Following a 2-week screening period, approximately 30 subjects will be randomly assigned into one of the following two arms in a 2:1 ratio (2 JointStem : 1 positive control):

- JointStem (1x10^8 cells/3mL)
- Positive control: Synvisc-One®

After each subject completes 6-month visit (Visit 6) and the data management team confirms all individual data have no issue, the individual database will be locked and the blinding will be open for the statistical analysis. Only subjects who are randomized to JointStem group will then be scheduled for 9-month and 12-month follow-up visits (Visits 7 and 8).

Long-term follow-up visit will be conducted to collect long-term feedbacks (records of medications and treatments) following 2 years after injection for all subjects who complete 6-month visit and accept the long-term follow-up visit.

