**Study Procedures:**

Visit 1 (Week -7) – Screening  
Visit 2 (Week -5) – Harvest of Adipose Tissue  
Visit 3 (Week 0) – Baseline (intra-articular injection)  
Visit 4 (Month 1) – 1-month follow-up  
Visit 5 (Month 3) – 3-month follow-up  
Visit 6 (Month 6) – 6-month follow-up (completion of treatment)  
\* *Double-blinding will end individually.*  
Visit 7 (Month 9) – 9-month follow-up (for only JointStem group)  
Visit 8 (Month 12) – 12-month follow-up (for only JointStem group)  
Long-term Follow-up (Month 24) – 24-month follow-up

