#### **4.2.6 Visit 6 (Months 6 ± 1 week)**

During this visit, the following assessments/procedures should be performed:

- The following questionnaires/procedures will be completed: WOMAC (see Appendix 3), VAS (see Appendix 4), Lysholm scale (see Appendix 5), KOOS (see Appendix 6), IKDC (see Appendix 7), and RAND-36 (see Appendix 8).
- Measure vital signs (sitting blood pressure, pulse, breathing, and temperature) and weight.
- Record any adverse event and any change in concomitant medications.

- Perform a complete physical examination.
- Measure 12-lead ECG.
- Collect blood and urine samples for hematology, serum chemistry, and urinalysis.
- Perform MRI measurement (Please follow the collection instruction separately provided by the sponsor).
- Dispense a concomitant medication note.

*\* After each subject completes Visit 6 (Month 6) and the data management team confirms all individual data have no issue, the individual database will be locked and the blinding will be open for the statistical analysis. Only subjects who are randomized to JointStem will be scheduled for Visits 7 and 8 (Months 9 and 12).*

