## **6.2 Determination of Sample Size**

There was no formal sample size calculation since this is a proof-of-concept study and is not a hypothesis-driven study. The number of enrolled subjects is predefined at n=30, for 20 subjects per study group and 10 subjects per control group.

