## **6.3 Interim Analysis**

When at least 15 subjects complete 6-month visits (Visit 6, Month 6), one unblinded interim analysis can be performed to evaluate the efficacy and safety of JointStem without the suspension of subject enrollment. The details of this interim analysis will be presented in the statistical analysis plan. No adjustment on the overall alpha-level will be made, as this is not a statistically powered study.

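### Codes open subject by subject at Month 6 while later subjects await the investigator's co-primary MRI rating; if the 2:1 list is restricted, some of their arms can be deduced.

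*Protocol*

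**What the plan says.** Opening is individual. The list of visits in the Protocol synopsis notes at Visit 6 that "Double-blinding will end individually". Protocol 4.2.6 says that, once that subject's data are confirmed, "the individual database will be locked and the blinding will be open for the statistical analysis". Protocol 3.5.6 has the same rule: after each subject's Visit 6 and data check, "the randomization code will be open for the statistical analysis". SAP 1.3.1 and 1.3.2 carry it too.

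No sentence says that the code is sent to the site. The site learns the arm all the same: Protocol 3.5.8 and 4.2.6 bring back only JointStem subjects at Months 9 and 12, and the schedule of assessments marks those visits as open.

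The third co-primary endpoint is a three-category MRI judgement by the Principal Investigator, based on a radiologist's report (Protocol 3.6.1 and 6.1.4). It succeeds if at least 36% of JointStem subjects are rated improved. Nothing in either document keeps the rater or the radiologist away from opened codes.

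On allocation, the synopsis gives a 2:1 ratio for approximately 30 subjects, and Protocol 6.2 states: "The number of enrolled subjects is predefined at n=30, for 20 subjects per study group and 10 subjects per control group". Block size, stratification and list type are left to a separate randomization instruction (Protocol 4.2.1). Protocol 3.5.3 places the efficacy analysis after the last subject's Visit 6. Protocol 6.3 allows one unblinded interim analysis from 15 Month 6 completers.

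**The concern.** In a permuted block or a closed 20:10 list, known assignments carry information about unknown ones. In a block of 3 at 2:1, one opened control code shows that the other two subjects are JointStem, and any two opened codes fix the third. An investigator who sees which earlier subjects go on to Visits 7 and 8 could therefore work out the arm of a subject whose Month 6 MRI is still to be rated.

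The MRI criterion is where this matters most. It is a judgement, it counts JointStem subjects only, and it is compared with a fixed cut-off. Generous rating of subjects known to be on JointStem is therefore not offset by anything in the control arm.

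A second consequence does not depend on the block size. Protocol 6.1.1.2 and SAP 2.2.2 allow further per-protocol criteria as long as the study database has not been unblinded. With rolling opening to the analysis, many codes may already be known when such criteria are written, and the safeguard loses much of its meaning.

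**Working it through.** **The plan's own figure.** 30 × 2/3 = 20 and 30 × 1/3 = 10, which agrees with Protocol 6.2.

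**Upper bound on the determinable share.** Assume that every earlier code in the list is already open, the rater sees all of them, and the rater knows the block size and list order. A subject's arm is then certain exactly when that subject lies in the closing run of a single arm within the block. For a block with J JointStem and C control places, the expected length of that run is J/(C+1) + C/(J+1), of which J/(C+1) are JointStem.

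| List (assumed) | Expected closing run | Share of all subjects | JointStem subjects known, of 20 |
|---|---|---|---|
| Unrestricted 2:1 | none | 0% | 0 |
| One list of 30 (20:10) | 20/11 + 10/21 = 2.29 | 2.29/30 = 8% | 1.8 |
| Blocks of 6 (4:2) | 4/3 + 2/5 = 1.73 | 1.73/6 = 29% | 6.7 |
| Blocks of 3 (2:1) | 2/2 + 1/3 = 1.33 | 1.33/3 = 44% | 10.0 |

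**If each site sees only its own codes** (one central list, blocks of 3, equal sites, no lag). The second subject in a block is determined if the first is at the same site and is a control. The third is determined if both others are at the same site, or if exactly one is and that one is a control.
- Three sites: (0 + 1/9 + 7/27)/3 = 12%.
- Two sites: (0 + 1/6 + 5/12)/3 = 19%.

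**If opening lags the visit.** Simulation with 30 subjects, uniform accrual over 6 to 24 months (assumed) and blocks of 3:
- No lag: about 44 to 45% with one list, about 41% with three site lists.
- Half a month: about 6 to 27% with one list, 20 to 34% with three site lists.
- One month: about 1 to 17% and 10 to 29%.

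A delay in rating the MRI would push these figures back up.

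**Effect on the MRI criterion (illustration).** 0.36 × 20 = 7.2, so 8 of 20 must be rated improved. Assume a true improvement rate of 25% and a rating probability 0.20 higher in subjects known to be on JointStem. Neither figure is in the documents. The chance of meeting the criterion is then:
- none known: 10.2%
- 2 known: 14.3%
- 6 known: 25.5%
- 9 known: 36.0%

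**Effect of deferring release to the site.** If a code opens about 2.75 months after Visit 6, shortly before Visit 7, the determinable share in the same simulation falls to 0 to 3% with one list and 0 to 15% with three site lists. The higher figures come with small blocks and slow accrual.

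**The case against.** The strongest objection is that deduction needs restricted randomization, a known block size and known list positions, and the documents give none of these. A target of 20 and 10 does not establish blocking, particularly when the synopsis speaks of approximately 30. That stands, so every share above is conditional and the low end is zero. The rule also requires data confirmation and an individual lock before opening, so the no-lag figures are upper bounds, and a subject's own Visit 6 data are protected. Only later subjects are exposed.

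Three stronger readings are tempting but not supported.
- A reader might infer that the Month 6 between-arm comparison is open to rater bias. Its endpoints are WOMAC, VAS, KOOS, Lysholm, IKDC and RAND-36 (Protocol 3.6.1), which subjects complete alone (Protocol 3.6.5). MRI is not among them.
- A reader might infer bias in concomitant treatment or in adverse event attribution. That requires knowing the arm well before Month 6. Knowledge at least a month ahead reaches 20 to 29% only with blocks of 3 by site, 12 to 24 months of accrual and no lag.
- A reader might take Protocol 6.3 to show that enrolment will still be running at 15 completers. It only permits an interim look "efficacy and safety of JointStem without the suspension of subject enrollment", and the synopsis speaks of the schedule of assessments instead.

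The study is also a proof of concept without a formal sample size. That lowers the priority, but it does not make early opening necessary.

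**Conclusion.** The concern holds in a limited form. The documents establish individual opening, site knowledge of the arm through the JointStem-only visits, and an investigator-rated co-primary endpoint with no stated separation of the rater from opened codes. They do not establish how many later arms can be deduced. The range is 0% for an unrestricted list, about 8% for one list of 30, and at most 29% or 44% for blocks of 6 or 3. Those maxima rest on no lag, a known block size and sight of all codes. With blocks of 3 from one central list and each site seeing only its own codes, the share is about 12% (three sites) or 19% (two).

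The endpoint mainly at risk is the 36% MRI criterion. Against this, early opening serves no stated statistical need apart from the optional interim, and it weakens the condition on adding per-protocol criteria. This is a worthwhile, inexpensive improvement rather than a fatal flaw.

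**What to change.** In Protocol 3.5.6 and 4.2.6 and SAP 1.3.2, with the matching synopsis and SAP 1.3.1 text aligned, replace opening at Visit 6 with wording to this effect:

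*No randomization code is released to the analysis before the last subject has completed Visit 6 and the database is locked, apart from the interim analysis if it is performed. A subject's code is not released to the site until it is needed to book Visit 7, and only after that subject's Month 6 MRI evaluation form has been signed.*

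Where existing staffing allows, add that opened codes are held by scheduling staff who do not rate MRI. This addresses the route that deferral leaves open.

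The change needs protocol and SAP wording only, with no added visits or assessments. Control subjects would learn their arm up to about 12 weeks later than now, and Visit 7 would be booked at shorter notice. Protocol 3.5.7 carries some restrictions to a 12-month visit that control subjects do not attend under 3.5.8. Those passages should be reconciled when the timing of disclosure to controls is settled. Deferral reduces the exposure but does not remove it: 0 to 15% of subjects may still be determinable with small blocks by site.
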